1.4 Hyperthyroidism

Cases including events of hyperthyroidism are retrieved from the safety database for analysis if they contain an event PT within the ‘Hyperthyroidism’ SMQ (broad scope), i.e., any of the following MedDRA PTs:

ANTI-THYROID ANTIBODY
ANTI-THYROID ANTIBODY DECREASED
ANTI-THYROID ANTIBODY POSITIVE
ANTITHYROID ARTHRITIS SYNDROME
AUTOIMMUNE THYROID DISORDER
AUTOIMMUNE THYROIDITIS

BASEDOW'S DISEASE
BIOPSY THYROID GLAND ABNORMAL
BLOOD THYROID STIMULATING HORMONE ABNORMAL
BLOOD THYROID STIMULATING HORMONE DECREASED
BLOOD THYROID STIMULATING HORMONE INCREASED
BUTANOL-EXTRACTABLE IODINE DECREASED
BUTANOL-EXTRACTABLE IODINE INCREASED
CONGENITAL THYROID DISORDER
ENDOCRINE OPHTHALMOPATHY
EUTHYROID SICK SYNDROME
EXOPHTHALMOS
FREE THYROXINE INDEX ABNORMAL
FREE THYROXINE INDEX DECREASED
FREE THYROXINE INDEX INCREASED
GAMMA RADIATION THERAPY TO THYROID
GOITRE
HASHIMOTO'S ENCEPHALOPATHY
HASHITOXICOSIS
HYPERTHYROIDISM
IMMUNE-MEDIATED HYPERTHYROIDISM
IMMUNE-MEDIATED THYROIDITIS
INAPPROPRIATE THYROID STIMULATING HORMONE SECRETION
INFECTIOUS THYROIDITIS
IODINE UPTAKE ABNORMAL
IODINE UPTAKE DECREASED
IODINE UPTAKE INCREASED
MALIGNANT EXOPHTHALMOS
MARINE LENHART SYNDROME
ORBITAL DECOMPRESSION
PHOTON RADIATION THERAPY TO THYROID
POLYGLANDULAR AUTOIMMUNE SYNDROME TYPE II
POLYGLANDULAR AUTOIMMUNE SYNDROME TYPE III
PRIMARY HYPERTHYROIDISM
PROTEIN BOUND IODINE DECREASED
PROTEIN BOUND IODINE INCREASED
RADIOACTIVE IODINE THERAPY
RADIOTHERAPY TO THYROID
REVERSE TRI-IODOTHYRONINE DECREASED
REVERSE TRI-IODOTHYRONINE INCREASED
SECONDARY HYPERTHYROIDISM
SILENT THYROIDITIS

THYREOSTATIC THERAPY
THYROGLOBULIN ABSENT
THYROGLOBULIN DECREASED
THYROGLOBULIN INCREASED
THYROGLOBULIN PRESENT
THYROID AUTOTRANSPLANTATION
THYROID DERMATOPATHY
THYROID DISORDER
THYROID DYSFUNCTION IN PREGNANCY
THYROID ELECTRON RADIATION THERAPY
THYROID FUNCTION TEST ABNORMAL
THYROID GLAND SCAN ABNORMAL
THYROID HEMIAGENESIS
THYROID HORMONE REPLACEMENT THERAPY
THYROID HORMONES INCREASED
THYROID OPERATION
THYROID PAIN
THYROID RELEASING HORMONE CHALLENGE TEST ABNORMAL
THYROID STIMULATING IMMUNOGLOBULIN INCREASED
THYROID THERAPY
THYROID TUBERCULOSIS
THYROIDECTOMY
THYROIDITIS
THYROIDITIS ACUTE
THYROIDITIS CHRONIC
THYROIDITIS FIBROUS CHRONIC
THYROIDITIS SUBACUTE
THYROTOXIC CARDIOMYOPATHY
THYROTOXIC CRISIS
THYROTOXIC MYOPATHY
THYROTOXIC PERIODIC PARALYSIS
THYROXIN BINDING GLOBULIN ABNORMAL
THYROXIN BINDING GLOBULIN DECREASED
THYROXIN BINDING GLOBULIN INCREASED
THYROXINE ABNORMAL
THYROXINE DECREASED
THYROXINE FREE ABNORMAL
THYROXINE FREE DECREASED
THYROXINE FREE INCREASED
THYROXINE INCREASED
THYROXINE THERAPY

TOXIC GOITRE
TOXIC NODULAR GOITRE
TRI-IODOTHYRONINE ABNORMAL
TRI-IODOTHYRONINE DECREASED
TRI-IODOTHYRONINE FREE ABNORMAL
TRI-IODOTHYRONINE FREE DECREASED
TRI-IODOTHYRONINE FREE INCREASED
TRI-IODOTHYRONINE FREE NORMAL
TRI-IODOTHYRONINE INCREASED
TRI-IODOTHYRONINE UPTAKE ABNORMAL
TRI-IODOTHYRONINE UPTAKE DECREASED
TRI-IODOTHYRONINE UPTAKE INCREASED
ULTRASOUND THYROID ABNORMAL
X-RAY THERAPY TO THYROID

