### C) Hyperthyroidism

Hyperthyroidism has been observed in 1% of the participants treated with selexipag in the GRIPHON study [Uptravi® USPI, Uptravi® SmPC].

The investigator is asked to inform the participants and the parents and provide guidance that they should be proactive and report if, at any time during study treatment, the participant experiences clinical signs of hyperthyroidism (eg, sudden weight loss even if appetite and the amount and type of food remain the same or even increased), tachycardia, arrhythmia or palpitations, nervousness, anxiety and irritability, tremor, sweating, an enlarged thyroid gland, difficulty sleeping).

If the participant experiences new or worsening of pre-existing hyperthyroidism during the course of treatment with study medication that, in the opinion of the investigator, cannot be adequately controlled with anti-thyroid medications, the study drug must be permanently discontinued and the participant monitored until resolution of this condition.

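### The Hyperthyroidism AESI uses an unpruned broad-scope query, so its total and rate can include events that point to low or normal thyroid function

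*SAP*

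**What the plan says.** SAP Appendix 2, section 1.4 retrieves hyperthyroidism cases with the Hyperthyroidism "SMQ (broad scope), i.e., any of the following MedDRA PTs", and then prints the list without exclusions. Among the entries are "BLOOD THYROID STIMULATING HORMONE INCREASED", "THYROXINE DECREASED", "THYROXINE FREE DECREASED", "THYROID HORMONE REPLACEMENT THERAPY", "THYROXINE THERAPY" and "TRI-IODOTHYRONINE FREE NORMAL".

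SAP section 4.1 sets out how each AESI category is used:

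- the percentage of participants with at least one occurrence, by system organ class, preferred term and age cohort;
- tabulations by severity, presented by treatment period, age cohort, body weight and overall;
- a summary by relationship to study drug;
- an average annualised event rate in which every repeat occurrence counts.

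Section 4.1 states a preferred-term breakdown for the first of these only.

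The protocol describes the known signal in the other direction. Section 1.2.3.4.2 reports more hyperthyroidism on selexipag than on placebo in GRIPHON, with small falls in TSH. Section 5.1.10 C adds: "Hyperthyroidism has been observed in 1% of the participants treated with selexipag in the GRIPHON study".

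**The concern.** The category carries a one-direction name, but its rule admits events in the opposite direction. A raised TSH reported as an adverse event would add to the same figure as a suppressed TSH. Where preferred terms are not shown, a reader could not tell the two apart.

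Such events are plausible here. Table 4 schedules TSH at baseline and Weeks 4, 12 and 16, and Table 5 schedules it at every later site visit and at end of treatment. Protocol section 7.2.4.1 requires clinically relevant laboratory abnormalities to be reported as adverse events. Exclusion criterion 14 bars only uncontrolled thyroid disease, so a child with controlled thyroid disease may enter.

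At stake is how clearly the trial reports a known risk of the drug in small paediatric cohorts, where one child moves a percentage visibly.

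**Working it through.** The documents state no rate, power or sample size for this AESI, so there is no figure of the plan's own to reproduce. The check has three parts.

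**1. Classify the printed list (SAP Appendix 2, section 1.4).** The list has 102 distinct preferred terms. Read by their wording, nine run against hyperthyroidism or are neutral to it:

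- Low-function laboratory terms (6): TSH increased; free thyroxine index decreased; thyroxine decreased; free thyroxine decreased; tri-iodothyronine decreased; free tri-iodothyronine decreased.
- Replacement-therapy terms (2): thyroid hormone replacement therapy; thyroxine therapy.
- Normal result (1): free tri-iodothyronine normal.

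6 + 2 + 1 = 9, and 102 − 9 = 93 remain. Iodine uptake, thyroglobulin, binding-globulin and the various 'abnormal' terms were left as ambiguous and are not among the nine. No term in the list names hypothyroidism or myxoedema.

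**2. Compare with neighbouring definitions in the same appendix.**

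- Section 1.1 (anaemia) uses broad-scope queries but takes two unspecific terms out of one of them.
- Section 1.3 (gastrointestinal disturbances) removes one irrelevant term that its text search would catch.
- Section 1.10 (pregnancy) removes negative and false-positive pregnancy test terms.
- Section 1.4 (hyperthyroidism) removes nothing and retains a normal result.

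Pruning is therefore already part of how this appendix is written.

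**3. Size of one miscounted child.** SAP section 1.2 plans about 60 participants, about 20 per cohort. The added percentage is k/n, where k is an assumed number of children whose only listed event is one of the nine terms:

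| k | n = 60 | n = 20 |
|---|---|---|
| 1 | 1.7% | 5.0% |
| 2 | 3.3% | 10.0% |
| 3 | 5.0% | 15.0% |

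The documents give no basis for choosing k, so the table shows leverage and does not forecast. No figure is given for the annualised rate, because the documents do not state the participant-years that form its denominator.

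**The case against.** The strongest points on the other side are these.

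- **Direction stays visible in places.** The main AESI table has preferred-term rows, so a raised TSH appears under its own name. SAP section 4.3 presents TSH, thyroid antibodies, free T3 and free T4 separately. SAP section 4.2 gives high and low flags and shift tables, and change in TSH is a safety endpoint (protocol section 6.2). This stands and confines the problem to category totals and the outputs built on them. It does not remove it: the laboratory output is not an event count, and the marked-abnormality table in section 4.2 sets no limits for TSH, T3 or T4.
- **Three of the nine terms are unlikely to occur.** A normal result hardly meets the adverse-event definition in protocol section 9.1.1. Treatments are recorded as concomitant therapy (protocol section 5.2) and coded with the WHO drug dictionary (SAP section 3.3). This stands; the realistic exposure is the six laboratory terms, chiefly raised TSH.
- **Broad scope is a declared choice.** Section 1.4 says so openly, and SAP Amendment 1 aligned the AESI definitions with the selexipag programme. This stands, and is a reason to keep the broad total.
- **No decision rests on it.** Safety analysis is descriptive, and the discontinuation rule in protocol section 5.1.10 C depends on clinical judgement, not on this rate. This stands and limits the consequence.

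Two stronger readings are tempting. A reader might infer that hypothyroid children will be reported as hyperthyroid. The documents do not support that: an event coded to hypothyroidism is not on the list, and only certain laboratory or therapy codings are caught. A reader might also infer that one such child exceeds the adult 1% and spoils a comparison with it. But 1/60 exceeds 1% for any single event of any kind, the SAP plans no such comparison, and the documents do not say which terms produced the adult figure.

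**Conclusion.** The concern holds in a limited form. The Hyperthyroidism total, and the severity, relationship and annualised-rate outputs drawn from it, can mix opposite directions under a one-direction label. The category is also neither a hyperthyroidism measure nor a general thyroid measure, since it takes raised TSH but not hypothyroidism. The total is harder to interpret than it need be, but it is not uninterpretable, because direction can be recovered from the preferred-term rows and the thyroid laboratory output.

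Each such child would add about 1.7 points overall or 5 points in a cohort of 20. This assumes the planned enrolment, at least one reported event of this kind, and no other listed event in that child. The classification of the nine terms rests on their wording and needs clinical confirmation. This is a cheap improvement in reporting, not a flaw that affects the trial's conclusions on dose.

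**What to change.** Keep the current list and its total for programme consistency, but label it 'Hyperthyroidism SMQ (broad)' in every output. Beside it, add a prespecified direction-consistent hyperthyroidism subset: hyperthyroid diagnoses, TSH decreased, T4 or T3 increased, and anti-thyroid therapy. Report the percentage, severity, relationship and annualised-rate outputs for both. Ambiguous terms stay in the broad total only. Retaining the combined total matters because a child may have events of both kinds, so two separate rows could not simply be added.

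The cost is an edit to SAP Appendix 2 and one extra row per output; no new data are needed. The term classification needs clinical sign-off. Because the study is open-label and data were already cut on 04MAY2020 for the Canadian submission (SAP section 2.3), the amendment should record that the subset was added after that cut.

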1.5 Hypotension

"The case will be included in this subgroup if it contains an event with any of the following MedDRA Preferred Terms:

BLOOD PRESSURE AMBULATORY DECREASED
BLOOD PRESSURE DECREASED
BLOOD PRESSURE DIASTOLIC DECREASED
BLOOD PRESSURE IMMEASURABLE
BLOOD PRESSURE ORTHOSTATIC DECREASED
BLOOD PRESSURE SYSTOLIC DECREASED
BLOOD PRESSURE SYSTOLIC INSPIRATORY DECREASED
CT HYPOTENSION COMPLEX
DIALYSIS HYPOTENSION
DIASTOLIC HYPOTENSION
HYPOTENSION
HYPOTENSIVE CRISIS
MEAN ARTERIAL PRESSURE DECREASED
NEONATAL HYPOTENSION
ORTHOSTATIC HYPOTENSION
POST PROCEDURAL HYPOTENSION
PROCEDURAL HYPOTENSION

1.6 Light-dependent non-melanoma skin malignancies

Cases including events denoting non-melanoma skin malignancies are retrieved from the safety database for analysis if they contain an event PT within the MedDRA High Level Term ‘Skin neoplasms malignant and unspecified (excl. melanoma)’, or if they contain the MedDRA PT ‘Squamous cell carcinoma’, i.e., any of the following MedDRA PTs:

ATYPICAL FIBROXANTHOMA

BASAL CELL CARCINOMA
BASAL CELL CARCINOMA METASTATIC
BASAL CELL NAEVUS SYNDROME
BASOSQUAMOUS CARCINOMA OF SKIN
BOWEN'S DISEASE
CARCINOMA IN SITU OF SKIN
DYSPLASTIC NAEVUS SYNDROME
ECCRINE CARCINOMA
EPIDERMAL NAEVUS SYNDROME
EXTRAMAMMARY PAGET'S DISEASE
HIDRADENOCARCINOMA
KERATOACANTHOMA
MALIGNANT SWEAT GLAND NEOPLASM
MARJOLIN'S ULCER
MASTOCYTOMA
NEOPLASM SKIN
NEUROENDOCRINE CARCINOMA OF THE SKIN
PILOMATRIX CARCINOMA
POROCARCINOMA
SEBACEOUS CARCINOMA
SKIN ANGIOSARCOMA
SKIN CANCER
SKIN CANCER METASTATIC
SKIN NEOPLASM BLEEDING
SKIN SQUAMOUS CELL CARCINOMA METASTATIC
SKIN SQUAMOUS CELL CARCINOMA RECURRENT
SQUAMOUS CELL CARCINOMA
SQUAMOUS CELL CARCINOMA OF SKIN
TRICHOBLASTIC CARCINOMA

1.7 Major adverse cardiovascular events

Cases including major adverse cardiovascular events (MACE) are retrieved from the safety database for analysis if they contain an event PT within any of the following MedDRA SMQs: 'Conditions associated with central nervous system haemorrhages and cerebrovascular accidents' (broad scope), 'Haemorrhagic central nervous system vascular conditions' (narrow scope), 'Ischaemic central nervous system vascular conditions' (narrow scope), or 'Myocardial infarction' (narrow scope), or an event with any of the following MedDRA PTs: 'Cardiac arrest', 'Cardiac death', 'Cardio-respiratory arrest', 'Coronary artery disease', 'Coronary artery insufficiency', 'Coronary vein stenosis', 'Myocardial ischaemia', 'Pseudostroke', 'Sudden cardiac death', and 'Sudden death', i.e., any of the following MedDRA PTs:

ACUTE CARDIAC EVENT
ACUTE CORONARY SYNDROME

ACUTE MYOCARDIAL INFARCTION
AGNOSIA
AMAUROSIS FUGAX
ANGINA UNSTABLE
ANGIOGRAM CEREBRAL ABNORMAL
APHASIA
BALINT'S SYNDROME
BASAL GANGLIA HAEMATOMA
BASAL GANGLIA HAEMORRHAGE
BASAL GANGLIA INFARCTION
BASAL GANGLIA STROKE
BASILAR ARTERY ANEURYSM
BASILAR ARTERY OCCLUSION
BASILAR ARTERY PERFORATION
BASILAR ARTERY STENOSIS
BASILAR ARTERY THROMBOSIS
BENEDIKT'S SYNDROME
BLOOD CREATINE PHOSPHOKINASE MB ABNORMAL
BLOOD CREATINE PHOSPHOKINASE MB INCREASED
BRACHIOCEPHALIC ARTERIOSCLEROSIS
BRACHIOCEPHALIC ARTERY OCCLUSION
BRACHIOCEPHALIC ARTERY STENOSIS
BRAIN HYPOXIA
BRAIN INJURY
BRAIN STEM EMBOLISM
BRAIN STEM HAEMATOMA
BRAIN STEM HAEMORRHAGE
BRAIN STEM INFARCTION
BRAIN STEM ISCHAEMIA
BRAIN STEM MICROHAEMORRHAGE
BRAIN STEM STROKE
BRAIN STEM THROMBOSIS
BRAIN STENT INSERTION
CADASIL
CAPSULAR WARNING SYNDROME
CARASIL SYNDROME
CARDIAC ARREST
CARDIAC DEATH
CARDIO-RESPIRATORY ARREST
CAROTID ANEURYSM RUPTURE
CAROTID ANGIOPLASTY

CAROTID ARTERIAL EMBOLUS
CAROTID ARTERIOSCLEROSIS
CAROTID ARTERY ANEURYSM
CAROTID ARTERY BYPASS
CAROTID ARTERY DISEASE
CAROTID ARTERY DISSECTION
CAROTID ARTERY INSUFFICIENCY
CAROTID ARTERY OCCLUSION
CAROTID ARTERY PERFORATION
CAROTID ARTERY RESTENOSIS
CAROTID ARTERY STENOSIS
CAROTID ARTERY STENT INSERTION
CAROTID ARTERY STENT REMOVAL
CAROTID ARTERY THROMBOSIS
CAROTID ENDARTERECTOMY
CAROTID REVASCULARISATION
CENTRAL NERVOUS SYSTEM HAEMORRHAGE
CENTRAL PAIN SYNDROME
CEREBELLAR ARTERY OCCLUSION
CEREBELLAR ARTERY THROMBOSIS
CEREBELLAR ATHEROSCLEROSIS
CEREBELLAR EMBOLISM
CEREBELLAR HAEMATOMA
CEREBELLAR HAEMORRHAGE
CEREBELLAR INFARCTION
CEREBELLAR ISCHAEMIA
CEREBELLAR MICROHAEMORRHAGE
CEREBELLAR STROKE
CEREBRAL ANEURYSM PERFORATION
CEREBRAL ANEURYSM RUPTURED SYPHILITIC
CEREBRAL ARTERIOSCLEROSIS
CEREBRAL ARTERIOVENOUS MALFORMATION HAEMORRHAGIC
CEREBRAL ARTERY EMBOLISM
CEREBRAL ARTERY OCCLUSION
CEREBRAL ARTERY PERFORATION
CEREBRAL ARTERY RESTENOSIS
CEREBRAL ARTERY STENOSIS
CEREBRAL ARTERY STENT INSERTION
CEREBRAL ARTERY THROMBOSIS
CEREBRAL CAVERNOUS MALFORMATION
CEREBRAL CYST HAEMORRHAGE

CEREBRAL ENDOVASCULAR ANEURYSM REPAIR
CEREBRAL GAS EMBOLISM
CEREBRAL HAEMATOMA
CEREBRAL HAEMORRHAGE
CEREBRAL HAEMORRHAGE FOETAL
CEREBRAL HAEMORRHAGE NEONATAL
CEREBRAL HAEMOSIDERIN DEPOSITION
CEREBRAL INFARCTION
CEREBRAL INFARCTION FOETAL
CEREBRAL ISCHAEMIA
CEREBRAL MICROEMBOLISM
CEREBRAL MICROHAEMORRHAGE
CEREBRAL MICROINFARCTION
CEREBRAL REPERFUSION INJURY
CEREBRAL REVASCULARISATION
CEREBRAL SEPTIC INFARCT
CEREBRAL SMALL VESSEL ISCHAEMIC DISEASE
CEREBRAL THROMBOSIS
CEREBRAL VASCULAR OCCLUSION
CEREBRAL VASOCONSTRICTION
CEREBRAL VENOUS THROMBOSIS
CEREBRAL VENTRICULAR RUPTURE
CEREBROVASCULAR ACCIDENT
CEREBROVASCULAR ACCIDENT PROPHYLAXIS
CEREBROVASCULAR DISORDER
CEREBROVASCULAR INSUFFICIENCY
CEREBROVASCULAR PSEUDOANEURYSM
CEREBROVASCULAR STENOSIS
CHARCOT-BOUCHARD MICROANEURYSMS
CLAUDE'S SYNDROME
CONGENITAL HEMIPARESIS
CORONARY ARTERY DISEASE
CORONARY ARTERY EMBOLISM
CORONARY ARTERY INSUFFICIENCY
CORONARY ARTERY OCCLUSION
CORONARY ARTERY REOCCLUSION
CORONARY ARTERY THROMBOSIS
CORONARY BYPASS THROMBOSIS
CORONARY VASCULAR GRAFT OCCLUSION
CORONARY VEIN STENOSIS
CSF BILIRUBIN POSITIVE

CSF RED BLOOD CELL COUNT POSITIVE
DELAYED ISCHAEMIC NEUROLOGICAL DEFICIT
DIPLEGIA
DYSARTHRIA
EMBOLIC CEREBELLAR INFARCTION
EMBOLIC CEREBRAL INFARCTION
EMBOLIC STROKE
EPIDURAL HAEMORRHAGE
EXTRA-AXIAL HAEMORRHAGE
EXTRADURAL HAEMATOMA
EXTRADURAL HAEMATOMA EVACUATION
EXTRAISCHAEMIC CEREBRAL HAEMATOMA
FOVILLE SYNDROME
HAEMORRHAGE INTRACRANIAL
HAEMORRHAGIC CEREBRAL INFARCTION
HAEMORRHAGIC STROKE
HAEMORRHAGIC TRANSFORMATION STROKE
HEMIANAESTHESIA
HEMIASOMATOGNOSIA
HEMIATAXIA
HEMIDYSAESTHESIA
HEMIHYPERAESTHESIA
HEMIPARAESTHESIA
HEMIPARESIS
HEMIPLEGIA
HUNT AND HESS SCALE
HYPOXIC-ISCHAEMIC ENCEPHALOPATHY
INNER EAR INFARCTION
INTERNAL CAPSULE INFARCTION
INTERNAL CAROTID ARTERY DEFORMITY
INTRA-CEREBRAL ANEURYSM OPERATION
INTRACEREBRAL HAEMATOMA EVACUATION
INTRACRANIAL ANEURYSM
INTRACRANIAL ARTERY DISSECTION
INTRACRANIAL HAEMATOMA
INTRACRANIAL TUMOUR HAEMORRHAGE
INTRAVENTRICULAR HAEMORRHAGE
INTRAVENTRICULAR HAEMORRHAGE NEONATAL
ISCHAEMIC CEREBRAL INFARCTION
ISCHAEMIC STROKE
KOUNIS SYNDROME

LACUNAR INFARCTION
LACUNAR STROKE
LATERAL MEDULLARY SYNDROME
LATEROPULSION
MENINGORRHAGIA
MIGRAINOUS INFARCTION
MILLARD-GUBLER SYNDROME
MODIFIED RANKIN SCORE DECREASED
MODIFIED RANKIN SCORE INCREASED
MONOPARESIS
MONOPLÉGIA
MOYAMOYA DISEASE
MYOCARDIAL INFARCTION
MYOCARDIAL ISCHAEMIA
MYOCARDIAL NECROSIS
MYOCARDIAL REPERFUSION INJURY
MYOCARDIAL STUNNING
NIH STROKE SCALE ABNORMAL
NIH STROKE SCALE SCORE DECREASED
NIH STROKE SCALE SCORE INCREASED
PAPILLARY MUSCLE INFARCTION
PARALYSIS
PARAPARESIS
PARAPLEGIA
PARESIS
PERINATAL STROKE
PERIPROCEDURAL MYOCARDIAL INFARCTION
PERIVENTRICULAR HAEMORRHAGE NEONATAL
PITUITARY APOPLEXY
PITUITARY HAEMORRHAGE
POST CARDIAC ARREST SYNDROME
POST PROCEDURAL MYOCARDIAL INFARCTION
POST PROCEDURAL STROKE
POST STROKE DEPRESSION
POSTHAEMORRHAGIC HYDROCEPHALUS
POSTINFARCTION ANGINA
PRECEREBRAL ARTERIOSCLEROSIS
PRECEREBRAL ARTERY EMBOLISM
PRECEREBRAL ARTERY OCCLUSION
PRECEREBRAL ARTERY THROMBOSIS
PSEUDOSTROKE

PUTAMEN HAEMORRHAGE
QUADRIPARESIS
QUADRIPLEGIA
REVERSIBLE CEREBRAL VASOCONSTRICTION SYNDROME
REVERSIBLE ISCHAEMIC NEUROLOGICAL DEFICIT
RIGHT HEMISPHERE DEFICIT SYNDROME
RUPTURED CEREBRAL ANEURYSM
SILENT MYOCARDIAL INFARCTION
SPINAL ARTERY EMBOLISM
SPINAL ARTERY THROMBOSIS
SPINAL CORD HAEMATOMA
SPINAL CORD HAEMORRHAGE
SPINAL CORD INFARCTION
SPINAL CORD ISCHAEMIA
SPINAL EPIDURAL HAEMATOMA
SPINAL EPIDURAL HAEMORRHAGE
SPINAL STROKE
SPINAL SUBARACHNOID HAEMORRHAGE
SPINAL SUBDURAL HAEMATOMA
SPINAL SUBDURAL HAEMORRHAGE
STROKE IN EVOLUTION
SUBARACHNOID HAEMATOMA
SUBARACHNOID HAEMORRHAGE
SUBARACHNOID HAEMORRHAGE NEONATAL
SUBCLAVIAN STEAL SYNDROME
SUBDURAL HAEMATOMA
SUBDURAL HAEMATOMA EVACUATION
SUBDURAL HAEMORRHAGE
SUBDURAL HAEMORRHAGE NEONATAL
SUDDEN CARDIAC DEATH
SUDDEN DEATH
SUPERFICIAL SIDEROSIS OF CENTRAL NERVOUS SYSTEM
THALAMIC INFARCTION
THALAMUS HAEMORRHAGE
THROMBOTIC CEREBRAL INFARCTION
THROMBOTIC STROKE
TRANSIENT ISCHAEMIC ATTACK
TROPONIN I INCREASED
TROPONIN INCREASED
TROPONIN T INCREASED
VASCULAR ENCEPHALOPATHY

VASCULAR STENT OCCLUSION
VASCULAR STENT STENOSIS
VEIN OF GALEN ANEURYSMAL MALFORMATION
VERTEBRAL ARTERY ANEURYSM
VERTEBRAL ARTERY ARTERIOSCLEROSIS
VERTEBRAL ARTERY DISSECTION
VERTEBRAL ARTERY OCCLUSION
VERTEBRAL ARTERY PERFORATION
VERTEBRAL ARTERY STENOSIS
VERTEBRAL ARTERY THROMBOSIS
VERTEBROBASILAR INSUFFICIENCY
VERTEBROBASILAR STROKE
VISUAL AGNOSIA
VISUAL MIDLINE SHIFT SYNDROME
WEBER'S SYNDROME

1.8 Medication errors

Cases with events of medication errors are retrieved from the safety database for analysis if they contain an event PT within the 'Medication errors' SMQ (narrow scope), i.e., any of the following MedDRA PTs:

ACCIDENTAL DEVICE INGESTION
ACCIDENTAL DEVICE INGESTION BY A CHILD
ACCIDENTAL EXPOSURE TO PRODUCT
ACCIDENTAL EXPOSURE TO PRODUCT BY CHILD
ACCIDENTAL EXPOSURE TO PRODUCT PACKAGING
ACCIDENTAL EXPOSURE TO PRODUCT PACKAGING BY CHILD
ACCIDENTAL OVERDOSE
ACCIDENTAL POISONING
ACCIDENTAL UNDERDOSE
ACCIDENTAL USE OF PLACEBO
BOOSTER DOSE MISSED
CIRCUMSTANCE OR INFORMATION CAPABLE OF LEADING TO DEVICE USE ERROR
CIRCUMSTANCE OR INFORMATION CAPABLE OF LEADING TO MEDICATION ERROR
CONTRAINDICATED DEVICE USED
CONTRAINDICATED PRODUCT ADMINISTERED
CONTRAINDICATED PRODUCT PRESCRIBED
DEPRESCRIBING ERROR
DEVICE DISPENSING ERROR
DEVICE MONITORING PROCEDURE NOT PERFORMED
DEVICE PROGRAMMING ERROR
DEVICE USE CONFUSION

DEVICE USE ERROR
DISCONTINUED PRODUCT ADMINISTERED
DOCUMENTED HYPERSENSITIVITY TO ADMINISTERED PRODUCT
DOSE CALCULATION ERROR
DRUG ADMINISTERED IN WRONG DEVICE
DRUG DISPENSED TO WRONG PATIENT
DRUG DOSE OMISSION BY DEVICE
DRUG DOSE TITRATION NOT PERFORMED
DRUG MONITORING PROCEDURE INCORRECTLY PERFORMED
DRUG MONITORING PROCEDURE NOT PERFORMED
DRUG TITRATION ERROR
DUPLICATE THERAPY ERROR
EXPIRED DEVICE USED
EXPIRED PRODUCT ADMINISTERED
EXPOSURE VIA DIRECT CONTACT
EXPOSURE VIA EYE CONTACT
EXPOSURE VIA SKIN CONTACT
EXTRA DOSE ADMINISTERED
FAILURE OF CHILD RESISTANT PRODUCT CLOSURE
FAILURE TO SUSPEND MEDICATION
INADEQUATE ASEPTIC TECHNIQUE IN USE OF PRODUCT
INAPPROPRIATE SCHEDULE OF PRODUCT ADMINISTRATION
INAPPROPRIATE SCHEDULE OF PRODUCT DISCONTINUATION
INCOMPLETE COURSE OF VACCINATION
INCORRECT DISPOSAL OF PRODUCT
INCORRECT DOSAGE ADMINISTERED
INCORRECT DOSE ADMINISTERED
INCORRECT DOSE ADMINISTERED BY DEVICE
INCORRECT DOSE ADMINISTERED BY PRODUCT
INCORRECT DRUG ADMINISTRATION RATE
INCORRECT PRODUCT ADMINISTRATION DURATION
INCORRECT PRODUCT DOSAGE FORM ADMINISTERED
INCORRECT PRODUCT FORMULATION ADMINISTERED
INCORRECT ROUTE OF PRODUCT ADMINISTRATION
INTERCEPTED ACCIDENTAL EXPOSURE TO PRODUCT BY CHILD
INTERCEPTED MEDICATION ERROR
INTERCEPTED PRODUCT ADMINISTRATION ERROR
INTERCEPTED PRODUCT DISPENSING ERROR
INTERCEPTED PRODUCT MONITORING ERROR
INTERCEPTED PRODUCT PREPARATION ERROR
INTERCEPTED PRODUCT PRESCRIBING ERROR

INTERCEPTED PRODUCT SELECTION ERROR
INTERCEPTED PRODUCT STORAGE ERROR
INTERCEPTED WRONG PATIENT SELECTED
LABELLED DRUG-DISEASE INTERACTION MEDICATION ERROR
LABELLED DRUG-DRUG INTERACTION MEDICATION ERROR
LABELLED DRUG-FOOD INTERACTION MEDICATION ERROR
LACK OF ADMINISTRATION SITE ROTATION
LACK OF APPLICATION SITE ROTATION
LACK OF INFUSION SITE ROTATION
LACK OF INJECTION SITE ROTATION
LACK OF VACCINATION SITE ROTATION
MEDICAL DEVICE MONITORING ERROR
MEDICATION ERROR
MULTIPLE USE OF SINGLE-USE PRODUCT
PARAVENOUS DRUG ADMINISTRATION
PRODUCT ADMINISTERED AT INAPPROPRIATE SITE
PRODUCT ADMINISTERED BY WRONG PERSON
PRODUCT ADMINISTERED TO PATIENT OF INAPPROPRIATE AGE
PRODUCT ADMINISTRATION ERROR
PRODUCT APPEARANCE CONFUSION
PRODUCT BARCODE ISSUE
PRODUCT CONFUSION
PRODUCT DESIGN CONFUSION
PRODUCT DISPENSING ERROR
PRODUCT DOSAGE FORM CONFUSION
PRODUCT DOSE OMISSION IN ERROR
PRODUCT LABEL CONFUSION
PRODUCT MONITORING ERROR
PRODUCT NAME CONFUSION
PRODUCT PACKAGING CONFUSION
PRODUCT PREPARATION ERROR
PRODUCT PRESCRIBING ERROR
PRODUCT SELECTION ERROR
PRODUCT STORAGE ERROR
PRODUCT SUBSTITUTION ERROR
RECALLED PRODUCT ADMINISTERED
SINGLE COMPONENT OF A TWO-COMPONENT PRODUCT ADMINISTERED
THERAPEUTIC DRUG MONITORING ANALYSIS INCORRECTLY PERFORMED
THERAPEUTIC DRUG MONITORING ANALYSIS NOT PERFORMED
TRANSCRIPTION MEDICATION ERROR
TRANSFUSION WITH INCOMPATIBLE BLOOD

UNINTENTIONAL USE FOR UNAPPROVED INDICATION
VACCINATION ERROR
WRONG DEVICE USED
WRONG DOSAGE FORM
WRONG DOSAGE FORMULATION
WRONG DOSE
WRONG DRUG
WRONG PATIENT
WRONG PATIENT RECEIVED PRODUCT
WRONG PRODUCT ADMINISTERED
WRONG PRODUCT PROCURED
WRONG PRODUCT STORED
WRONG RATE
WRONG ROUTE
WRONG SCHEDULE
WRONG STRENGTH
WRONG TECHNIQUE IN DEVICE USAGE PROCESS
WRONG TECHNIQUE IN PRODUCT USAGE PROCESS

